4.3.2 V2: Day 1 assessment: 24 ± 6 hours after start of treatment

Clinical examination is performed as detailed for V1 except for body weight and height. All patients (control and intervention group) will receive a CT scan to assess the evolution of the hematoma volume (recurrent haemorrhage or postoperative hematoma reduction in case of the intervention group).

4.3.3 V3: Day 3 assessment: 72 ± 12 hours after treatment

Clinical examination is performed as detailed for V1 except for body weight and height. Blood sampling for biomarkers will be obtained.

4.3.4 V4: Day 7 assessment: 7±1 days after treatment or at hospital discharge

Clinical examination is performed as detailed for V1 except for body weight and height.

4.3.5 V5: Month 3 assessment: 3 months ± 14 days after treatment

Clinical examination is performed as detailed for V1 except for body weight and height and mRS. A MOCA Test is performed. Additionally, a questionnaire regarding patient satisfaction will be filled-out whenever possible through a relative or otherwise together with a member of the study team and patients and their relatives will be asked to fill out a questionnaire together with a member of the study team regarding quality of life. Additionally, patients are telephonically contacted by a study-team member (blinded to the allocation) to assess the mRS according to the form in Appendix 4.

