3 STUDY OBJECTIVES AND DESIGN

3.1 Hypothesis, primary and secondary objectives

The **Null hypothesis (H₀)** describes no difference in functional outcome rates of early minimally invasive image-guided endoscopic evacuation additionally to BMT for SSICH compared to BMT alone.

The **Alternative Hypothesis (H₁)** describes a difference (either improved or worsened [two-sided testing]) functional outcome rates of early minimally invasive image guided endoscopic evacuation additionally to BMT for SSICH compared to BMT alone.

The primary objective of this two, armed, open-labelled, single centre randomised controlled trial is to show superiority of early minimally invasive image-guided hematoma evacuation additionally to BMT compared to BMT alone in functional outcome rates at 6 months in patients with SSICH.

Secondary objectives are:

- to show superior survival rates of patients in the ES arm
- to study patient reported quality of life after treatment for SSICH at different time points (3 and 6 months after intervention)
- to study patient satisfaction with the outcome after treatment for SSICH at different time points (3 months and 6 months after intervention)
- to study cognitive outcome in patients after treatment for SSICH at different time points (3 months and 6 months after intervention)
- to study the morbidity rates of patients in both treatment arms
- to study the efficacy of ES in reducing the hematoma volume
- to study the change in focal neurological deficits exhibited by the patients after treatment.
- to study the temporal evolution of serum biomarkers (Neurofilament light-chain subunit (NfL), Glial Fibrillary Acidic Protein (GFAP), S100 calcium-binding protein B (S100B), IL-1 α and β , IL-2, IL-4, IL-5, IL-6, IL-8, IL-10, IL-12p70 and TNF- α) and their change in relation to early hematoma ES.

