3.2 Primary and secondary outcomes

Primary outcome:

- Good functional outcome 6 months after treatment, measured by the mRS[33]. Good functional outcome is defined as a mRS of ≤ 3 points and will be assessed as binary outcome (yes/no, final value) at 6 months after treatment. The cut-off for good functional outcome is chosen at a mRS score of 3 points, as this reflects the turning point for a patient being able to live a partially self-dependent life or to live a severely disabled life. In this context, a mRS score of 3 points reflects the ability to walk unassisted and care for one's own bodily needs despite being moderately dependent on assistance, while a mRS score of 4 points describes a patient who is not able to walk anymore and needs assistance with all daily activities and thus marks a severe loss of patient autonomy.

Secondary outcomes:

- The mortality rate as measured by death of a participant (binary outcome (yes/no), final value) at 6 months after intervention.

- Patient reported outcome measures at 3 and 6 months after intervention, those being:
 - Patient and caregiver quality of life as assessed by the PROMIS® questionnaire (continuous variable, final value)
 - Patient Satisfaction as assessed by a short survey (Appendix 2) on a scale of 1-5 (continuous variable, final value)
 - Patient cognitive outcome as assessed by the MOCA® Test (continuous variable, final value)
- The morbidity rate, meaning occurrence of:
 - Ischemic stroke
 - Recurrent SSICH (defined as any radiologically confirmed increase in hematoma volume postoperative/follow-up that is either asymptomatic or associated with a worsening of the focal-neurological deficit by ≥ 4 points on the NIHSS and/or a decrease in consciousness by ≥ 2 points on the GCS)
 - Epileptic seizure
 - Surgical site infection (intervention group only)
 - Any need for open neurosurgical procedures
 - Infections (i.e. pneumonia, urinary tract infection)
 - Any other not defined complication that prolongs the hospital stay and/or leads to further treatment not envisaged in the original treatment plan.

The occurrence of any of these events 6 months after intervention (binary variable (occurrence/no occurrence), final value, proportion).

- The change of focal neurological deficit measured by the NIHSS, from baseline to 6 months after intervention as a continuous variable (continuous variable, change from baseline).

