4.3 Study procedures

The planned overall study duration including recruitment period and follow-up for each participant is limited to 6 months after first admission to the hospital ending with visit 6. The study schedule consists of 6 study visits (V1-V6), which follow the regular in- and outpatient visit schedule in patients with SSICH (clinical routine), including the following procedures with the respective time period mentioned. All data collection for this study will begin after informed consent was given.

All imaging studies, study visits, the neurological examinations (GCS, NIHSS, MOCA) and the clinical examination are part of the daily clinical practice routine for SSICH, while the study specific examinations will consist of mRS evaluation, assessing the quality of life, patient satisfaction (Appendix 2) and acquiring blood samples. Blood sample will consist of collecting an aliquot of approximately 2 x 5 ml blood serum at each indicated visit. The additional blood samples for the study will be taken, if possible, during daily routine while the patient will be in the hospital (V1 & V3). For the Follow-Up visit (V6), an additional puncture will be necessary to obtain the blood samples. The PROMs Quality of Life and patient satisfaction will be assessed additionally by providing a paper-form questionnaire to the patients and their relatives. If patients are not able to complete the questionnaire, relatives will be asked to provide data.

Collected data will be preserved in encoded form to be used in future studies, patients will be informed about the encoded retention of data and given a separate informed consent. All blood samples will be discarded after analysis and will not be used for future studies.

We designed this trial together with affected patients, caregivers and patient organization representatives (EUPATI-CH) in the scope of PPI as pragmatic as possible, meaning that all visits and procedures were meticulously evaluated. With this we are convinced, that patients will remain in the trial as it is only little, if any at all, expenditure more than what would be the standard of care. From patients that drop out, we will analyse the data until the point of drop-out (last visit present) in an intention-to-treat fashion. Likewise, if any deviation from intervention protocol should occur, the results will be analysed as intention-to-treat. Outcome data collected for drop-

outs will consist of all study data collected to the last visit.

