4.3.6 V6: Month 6 assessment: 6 months ± 7 weeks after treatment

Clinical examination is performed as detailed for V1 except for body weight and height and mRS. Blood sampling for biomarkers will be obtained. A cCT will be performed for all patients (control and intervention group) to evaluate possible rebleeding, hematoma resorption and the shape of the hematoma cavity. A MOCA Test is performed. Additionally, a questionnaire regarding patient satisfaction will be filled-out whenever possible through a relative or otherwise together with a member of the study team and patients and their relatives will be asked to fill out a questionnaire together with a member of the study team regarding the quality of life. Additionally, patients are telephonically contacted by a study-team member (blinded to the allocation) to assess the mRS according to the form in Appendix 4.

Study period	Treatment Period				Follow-Up	
Visit	1	2	3	4	5	6

Time (hour, day, week)	<24 hours of symptom onset	24 hours after treatment onset	72 hours after treatment onset	7 days after treatment onset	3 months after treatment onset	6 months after treatment onset
Eligibility	X					
Study consent	X					
Asses vital signs (BP,HR,height)	X	X	X	X	X	X
Acquire NIHSS score	X	X	X	X	X	X
Acquire GCS score	X	X	X	X	X	X
Acquire mRS score	X	X	X	X	X**	X**
Acquire blood samples (NfL, GFAP, S100B, IL)	X		X			X
Conduct Stability CT scan*	X					
Conduct directly postoperative CT scan†		X				
Conduct postinterventional CT scan‡		X				X
Quality of Life					X	X
Patient Satisfaction					X	X
Cognition					X	X

*intervention group only; only required if surgery cannot be initiated within 6 hours after the first cCT scan

†intervention group only; the directly postoperative cCT is conducted directly after surgery to assess hematoma evacuation and differentiate potential recurrent hemorrhage

‡all patients; the postinterventional cCT scan is conducted 24 hours and 6 months after the treatment start to assess potential recurrent/enlarged hematoma and defect size

**blinded telephone assessment

4.3.7 Additional material, storage, concomitant care as well as methods and tests used for sample collection and analysis

The imaging analysis, the additional materials and biomarkers used for this study and the procedure to reverse oral anticoagulation are explained in the following section.

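### The protocol gives relatives three different roles in the patient satisfaction form and two in PROMIS, with nothing that shows who answered, or about whom

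*Protocol*

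**What the plan says.** **Satisfaction form.** Section 4.3 covers satisfaction and quality of life together: "The PROMs Quality of Life and patient satisfaction will be assessed additionally by providing a paper-form questionnaire to the patients and their relatives". It then adds a fallback: "If patients are not able to complete the questionnaire, relatives will be asked to provide data". Section 4.3.5 sets a different order for satisfaction at month 3: "a questionnaire regarding patient satisfaction will be filled-out whenever possible through a relative or otherwise together with a member of the study team". Section 4.3.6 repeats this for month 6: "filled-out whenever possible through a relative or otherwise together with a member of the study team". Appendix 2 reports that the patient and public contributors proposed bringing relatives in as well when satisfaction is rated, because they expected more valid results. Section 3.2 lists the outcome as patient satisfaction, a single continuous score. The items in Appendix 3 are worded to the patient, and the form as shown has no field for who answered.

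**Quality of life.** The objective in section 3.1 is "to study patient reported quality of life after treatment for SSICH at different time points". The outcome line in section 3.2, repeated in the synopsis, is "Patient and caregiver quality of life as assessed by the" PROMIS questionnaire, again as one continuous variable. Section 4.3.5 says that "patients and their relatives will be asked to fill out a questionnaire together with a member of the study team regarding quality of life", and section 4.3.6 says the same for month 6. Section 4.3.7.2 names one PROMIS version and no proxy or caregiver version.

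**The concern.** A satisfaction score given by a relative is not the same measurement as one given by the patient. If the sections disagree about who should answer, staff following different sections will produce different raters for similar patients under one endpoint label.

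For PROMIS the difficulty is one of construct. A form completed by a relative may describe the relative's own health or stand in for the patient's. If the protocol does not say which, a relative's own score could be taken for the patient's, or the reverse.

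Both problems arise when the data are collected. An analysis plan can separate scores by rater only if the rater, and the person described, were recorded at the time. The need for someone else to answer also depends on the patient's condition, which the trial expects treatment to change, so the mix of raters may differ between arms.

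**Working it through.** The protocol gives no figure on this point, so the check is a comparison of the text.

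**Step 1: who completes the satisfaction form.**

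| Situation | Section 4.3 | Sections 4.3.5 and 4.3.6 | Appendix 2 |
|---|---|---|---|
| Patient able, relative available | Patient | Relative | Patient, with the relative as well |
| Patient able, no relative | Patient | Completed with a study-team member | Patient |
| Patient unable, relative available | Relative | Relative | Not addressed |
| Patient unable, no relative | Not addressed | Completed with a study-team member | Not addressed |

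The first row is the contradiction: three places give three answers. Section 4.3 does hand forms to both parties, but its next sentence makes the relative's data conditional on the patient being unable, which cannot be squared with a relative whenever possible. The second row also differs, since only 4.3.5 and 4.3.6 bring in study staff.

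**Step 2: whether the reversal extends to PROMIS.** It does not. Sections 4.3.5 and 4.3.6 ask patients and relatives alike to complete the quality-of-life form, with no order of preference. The conflict over order is confined to satisfaction.

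**Step 3: what a relative's PROMIS means.**

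- Under section 3.2 and the synopsis it is the caregiver's own quality of life.
- Under section 4.3 it can be data supplied because the patient could not complete the form.
- No section says which reading applies to a given form, names a proxy version, or says that the two are kept apart.

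**Step 4: whether the outcome definitions settle it.** They do not. Each outcome is one continuous score with no rater stated.

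**Step 5: whether a size can be derived.** The planning figures give good outcome in 50% of controls and 50% × 1.6 = 80% of the surgery arm (section 5.1.2.2). It is tempting to take the 30-point gap as the difference between arms in who can self-report. But those are shares of all randomised patients, and the dead return no forms. Assume, for illustration, that the 40-45% mortality in section 2 applied to controls and that every patient with good outcome could self-report:

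- controls: 0.50/0.60 = 83% to 0.50/0.55 = 91% of survivors;
- surgery arm, where 80% good outcome leaves 0-20% dead: 0.80/1.00 = 80% to 0.80/0.80 = 100% of survivors;
- gap (surgery minus control): 80 − 91 = −11 points to 100 − 83 = +17 points.

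Even the sign is open. The protocol gives no proxy-patient difference and no number of responders, so no bias can be computed.

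**The case against.** The strongest reply is that relatives were brought in deliberately. Appendix 2 gives a reason, and it came from patients and caregivers. That stands as a reason to collect relatives' ratings. It does not settle the order, because Appendix 2 adds relatives to the patient while 4.3.5 and 4.3.6 put them first.

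The next reply is that the protocol nowhere says patient and caregiver PROMIS scores will be pooled, and that separating them is ordinary work for a statistical analysis plan, which is not shown. This also stands in part. Pooling is something a reader might infer from the single outcome line, but the text does not state it. The defect is narrower: the relative's form has two possible meanings, and nothing in the protocol marks which one applies.

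Three stronger readings should be resisted.

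- *That relative-first completion biases the comparison because ability to self-report differs by arm.* The dependence runs mainly the other way. With the patient first and the relative as fallback, the share of proxy answers follows the patient's condition. With the relative first, and relatives equally available in both arms, the rater type is the same in both. This does not justify contradictory rules, but it means a patient-first rule must come with a record of the rater.
- *That the satisfaction comparison shifts by 0.09-0.15 SD.* This is 0.30 times an assumed proxy difference of 0.3-0.5 SD. The 30-point imbalance ignores deaths, and the proxy difference is in no document.
- *That staff help inflates satisfaction, and that the paper form in 4.3 avoids this.* Section 4.3 does not say the form is completed unattended. Barring staff help would lose forms from impaired patients without a relative, which is itself missingness related to outcome.

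**Conclusion.** The point holds as an inconsistency in data collection with two parts. For satisfaction, sections 4.3, 4.3.5/4.3.6 and Appendix 2 give the relative three different roles, under an endpoint and items that refer to the patient. For PROMIS, a relative's form is both a caregiver outcome and a possible substitute for the patient's, with no means of telling which.

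The reach is limited. These are secondary outcomes, and section 4.3.7.2 itself says the satisfaction questionnaire is not validated in clinical trials. The primary outcome, mRS by blinded telephone assessment, and the sample size are untouched. Neither the size nor the direction of any bias can be obtained from the documents. The conclusion rests on the wording alone and on the form as shown in Appendix 3. It is worth correcting because the change is cheap and because information on who answered cannot be recovered by a later analysis if it was not collected.

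**What to change.** 1. State one completion order for the satisfaction form, identically in sections 4.3, 4.3.5 and 4.3.6. Patient first fits the stated objective. If relatives are kept for the reason in Appendix 2, collect their ratings in addition to the patient's own form, not in place of it.
2. Add a field to every form recording who answered: patient alone, patient with staff help, or proxy.
3. Collect caregiver PROMIS on a separately labelled form, list it as its own endpoint in section 3.2 and the synopsis, and state that it never replaces the patient's.
4. Report both outcomes by rater, with a sensitivity analysis with and without proxy answers. This is needed under a patient-first rule, because ability to self-report depends on outcome and so may differ by arm.

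The cost is some wording, one extra field per form, a label on the caregiver PROMIS, and a little more analysis. If relatives' satisfaction ratings are collected as well, there is one more short form for those families.

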4.3.6 V6: Month 6 assessment: 6 months ± 7 weeks after treatment

Clinical examination is performed as detailed for V1 except for body weight and height and mRS. Blood sampling for biomarkers will be obtained. A cCT will be performed for all patients (control and intervention group) to evaluate possible rebleeding, hematoma resorption and the shape of the hematoma cavity. A MOCA Test is performed. Additionally, a questionnaire regarding patient satisfaction will be filled-out whenever possible through a relative or otherwise together with a member of the study team and patients and their relatives will be asked to fill out a questionnaire together with a member of the study team regarding the quality of life. Additionally, patients are telephonically contacted by a study-team member (blinded to the allocation) to assess the mRS according to the form in Appendix 4.

Study period	Treatment Period				Follow-Up	
Visit	1	2	3	4	5	6

Time (hour, day, week)	<24 hours of symptom onset	24 hours after treatment onset	72 hours after treatment onset	7 days after treatment onset	3 months after treatment onset	6 months after treatment onset
Eligibility	X					
Study consent	X					
Asses vital signs (BP,HR,height)	X	X	X	X	X	X
Acquire NIHSS score	X	X	X	X	X	X
Acquire GCS score	X	X	X	X	X	X
Acquire mRS score	X	X	X	X	X**	X**
Acquire blood samples (NfL, GFAP, S100B, IL)	X		X			X
Conduct Stability CT scan*	X					
Conduct directly postoperative CT scan†		X				
Conduct postinterventional CT scan‡		X				X
Quality of Life					X	X
Patient Satisfaction					X	X
Cognition					X	X

*intervention group only; only required if surgery cannot be initiated within 6 hours after the first cCT scan

†intervention group only; the directly postoperative cCT is conducted directly after surgery to assess hematoma evacuation and differentiate potential recurrent hemorrhage

‡all patients; the postinterventional cCT scan is conducted 24 hours and 6 months after the treatment start to assess potential recurrent/enlarged hematoma and defect size

**blinded telephone assessment

4.3.7 Additional material, storage, concomitant care as well as methods and tests used for sample collection and analysis

The imaging analysis, the additional materials and biomarkers used for this study and the procedure to reverse oral anticoagulation are explained in the following section.

4.3.7.1 Imaging analysis

In this study we will conduct cCT scans:

- At admission (clinical routine, both groups)
- 6 hours after the admission scan if surgery is started >6 hours after the admission scan (clinical routine stability scan, intervention group only)
- Directly postoperative (clinical routine in this procedure, intra-operative or directly after surgery, intervention group only)
- At the first day after start of treatment (clinical routine in SSICH, both groups)
- At the visit after 6 months (clinical routine, both groups)

The cCT scans serve to assess the hematoma volume and to provide information about the hematoma reduction rate or increase in hematoma volume and possible rebleeding after surgery.

The pre-operative hematoma will be assessed with the $\frac{A * B * C}{2}$ formula for screening purposes due to its fast and broad applicability in emergency room settings and will then, in a second step, be validated with the neuronavigation software later on[34]. To analyse the often irregular-shaped and small postoperative hematoma volume (cCT scan directly after surgery (intervention)/ 24 hours after treatment onset(control)), the hematoma will be segmented, and its volume calculated manually on a BrainLab® planning station (or equivalent) by a trained member of the study team. Both hematoma volumes as calculated on the BrainLab® planning station (or equivalent) from cCTs at admission and directly postoperative/after 24 hours after treatment onset will be compared to assess the evolution of the hematoma volume. This increases the comparability as the $\frac{A * B * C}{2}$ formula struggles with small irregular shaped hematoma volumes.

4.3.7.2 Questionnaires

The questionnaires used in this study are the Montreal Cognitive Assessment, the PROMIS Scale v1.2 Global Health, and a questionnaire for patient satisfaction derived in our Patient and Public involvement meetings (Appendix 2 and 3). Both, MOCA and PROMIS are well established and validated questionnaires to assess cognition and quality of life respectively and were deemed the most effective and patient friendly by our PPI representatives[39, 40]. Further, the timepoint of assessment was discussed and decided upon with the PPI representatives. The questionnaire regarding patient satisfaction was created together with the PPI representatives by first collecting the most important aspects of patient satisfaction, which were then in a next step condensed to the 5 most important questions. This questionnaire is not validated in clinical trials, but a reflection of important PROMs and a product of intense collaboration with PPIs.

